## 2.7 Safety analyses

All safety analyses will be performed based on the FAS.

### 2.7.1 Adverse events (AEs)

AE summaries will include all AEs occurring during on treatment period. All AEs collected in the AE (e)CRF page will be listed along with the information collected on those AEs e.g. AE relationship to study drug, AE outcome etc. AEs with start date outside of on-treatment period will be flagged in the listings.

AEs will be summarized by number and percentage of subjects having at least one AE, having at least one AE in each primary system organ class (SOC) and for each preferred term (PT) using MedDRA coding (using the latest version available prior to clinical database lock) by maximum severity (based on Common Terminology Criteria for Adverse Events [CTCAE] grades version 4.03), and relation to study drug. A subject with multiple occurrences of an AE will be counted only once in the respective AE category. A subject with multiple CTCAE grades for the same preferred term will be summarized under the maximum CTCAE grade recorded for the event.

In AE summaries, the primary system organ class will be presented alphabetically and the preferred terms will be sorted within primary SOC in descending frequency.

AEs will be coded using MedDRA using the latest version available at the time of analysis and will be graded using Common Terminology Criteria for Adverse Events (CTCAE) version 4.03. The CTCAE represents a comprehensive grading system for reporting the acute and late effects of cancer treatments. CTCAE grading is by definition a 5-point scale generally corresponding to mild, moderate, severe, life threatening, and death. This grading system inherently places a value on the importance of an event, although there is not necessarily proportionality among grades (a grade 2 is not necessarily twice as bad as a grade 1). The CTCAE grade of 5 (death) is not used; rather, 'fatal' is collected as AE outcome and death information is also collected on a separate (e)CRF page.

The following AE summaries will be produced:

- AEs regardless of study drug relationship
- AEs suspected to be study drug related
- On-treatment deaths, by primary system organ class and preferred term
- SAEs regardless of study drug relationship
- SAEs suspected to be study drug related
- AEs associated with discontinuation of study drug
- AEs requiring dose adjustment or study drug interruption
- AEs requiring significant additional therapy
- AEs excluding SAEs

All AEs regardless of study drug relationship will be summarized.

### **2.7.1.1 Adverse events of special interest / grouping of AEs**

Adverse events of special interest (AESI) are defined as events (serious or non-serious) which are ones of scientific and medical concern specific to the sponsor's product or program, for which ongoing monitoring and rapid communication by the investigator to the sponsor may be appropriate. Such events may require further investigation in order to characterize and understand them.

Adverse events of special interest are defined on the basis of an ongoing review of the safety data. AESI are discussed in detail in the Investigator Brochure, and a list of Medical Dictionary for Regulatory Activities (MedDRA) preferred terms to flag as AESI's will be exported from the eCRS.

AESI for dabrafenib include:

- Hypersensitivity
- Complicated pyrexia and/or Grade 3 and Grade 4
- New primary/secondary malignancy
- Pre-renal and intrinsic renal failure
- Uveitis
- Hyperglycemia
- Pancreatitis

• AESI for trametinib include:

- Skin related toxicities
- Ocular events
- Cardiac related events
- Hepatic disorders
- Pneumonitis/interstitial lung disease
- Bleeding events
- Hypertension
- Hypersensitivity
- Venous thromboembolism (VTE)

• AESI for dabrafenib in combination with trametinib include:

- Skin related toxicities
- Ocular events
- Cardiac related events
- Hepatic disorders

- Pneumonitis/interstitial lung disease
- Bleeding events
- Hypertension
- Hypersensitivity
- Pyrexia
- New primary/secondary malignancy
- Pre-renal and intrinsic renal failure
- Uveitis
- Hyperglycemia
- Venous thromboembolism (VTE)
- Pancreatitis
- Neutropenia

## **2.7.2 Deaths**

On-treatment and all deaths will be separately summarized based on the number and percentage of subjects. The summary will include primary cause of death (disease under study, SAE related to study treatment, or other).

All deaths will be listed, post-treatment deaths will be flagged.

## **2.7.3 Laboratory data**

The summaries will include all assessments collected no later than 30 days after study drug discontinuation. All assessments will be listed and those collected later than 30 days after study drug discontinuation will be flagged in the listings.

All laboratory data will be listed by subject, and visit/time and if normal ranges are available abnormalities will be flagged. Summary statistics will be provided by visit/time. Shift tables using the low/normal/high/ (low and high) classification will be used to compare baseline to the worst on-treatment value.

Grading of laboratory values will be assigned programmatically as per NCI Common Terminology Criteria for Adverse Events (CTCAE) version 4.03. The calculation of CTCAE grades will be based on the observed laboratory values only, clinical assessments will not be taken into account.

CTCAE Grade 0 will be assigned for all non-missing values not graded as 1 or higher. Grade 5 will not be used.

For laboratory tests where grades are not defined by CTCAE v4.03, results will be categorized as low/normal/high based on laboratory normal ranges.

The following summaries will be generated separately for hematology, and biochemistry tests:

- Listing of all laboratory data with values flagged to show the corresponding CTCAE v4.03 grades if applicable and the classifications relative to the laboratory normal ranges.

For laboratory tests where grades are defined by CTCAE v4.03:

- Worst post-baseline CTCAE grade (regardless of the baseline status). Each subject will be counted only once for the worst grade observed post-baseline.
- Shift tables using CTCAE v4.03 grades to compare baseline to the worst on-treatment value.

For laboratory tests where grades are not defined by CTCAE v4.03:

- Shift tables using the low/normal/high/ (low and high) classification to compare baseline to the worst on-treatment value.

## 2.7.4 Other safety data

The summaries will include all assessments collected no later than 30 days after study drug discontinuation. All assessments will be listed and those collected later than 30 days after study drug discontinuation will be flagged in the listings.

### 2.7.4.1 ECG and cardiac imaging data

All ECG parameters will be listed by subject and visit/time, abnormalities will be flagged. Summary statistics will be provided by treatment and visit/time. Separate listing will be provided for QTcF. Average value will be used for time points with triplicate measurements, and will be included in the listing. Separate listings of QTcF will be produced for subjects with any QTcF>500 msec and/or QTcF change from baseline >60msec. In all listings, baseline value will be specified for each subject.

All ECG parameters change from baseline will be listed. Separate listing will be provided for QTc change from baseline.

Numeric values of ECG parameters will be summarised at baseline, planned visit and worst case post-baseline. Summary statistics will include count, mean, median, standard deviation, minimum, and maximum.

Categorical Analysis of QT/QTc interval data based on the number of subjects meeting or exceeding predefined limits in terms of absolute QT/QTc intervals or changes from baseline will be presented. In addition, a listing of these subjects will be produced (by treatment group).

QTcF shifts from baseline category will be produced for worst case post-baseline. The following categories will be used:

- <450msec
- 450-480 msec
- 481-500 msec
- >500 msec

Worst case post-baseline increase from baseline to the following categories will be summarized for QTcF:

- Any Grade Increase
- Increase to Grade 1 (450-480 msec)
- Increase to Grade 2 (481-500 msec)
- Increase to Grade 3/4 (>500 msec)

Note: 'Any Grade Increase' will include increase to Grade 1 (450-480), increase to Grade 2 (481-500), and increase Grade 3/4 (>=501).

QTcF increases from baseline of 31-60 msec and >60 msec will be summarized for worst-case post-baseline. Subjects with missing baseline values will be excluded from this summary.

All ECG findings will be listed. The worst-case post-baseline ECG findings will be summarised by frequency and percentage.

LVEF Absolute change from baseline in LVEF will be summarized at each scheduled assessment time and in the worst case post baseline. Only the post baseline assessments that used the same method (ECHO or MUGA) as the baseline assessments will be used to derive the change from baseline. The change from baseline will be categorized as follows:

- Any increase
- No change
- Any decrease
- >0 - < 10 Decrease
- 10 - 19 Decrease
- >= 20 Decrease

LVEF results will also be listed with subject level details including absolute change from baseline.

Note: If there is any change in the methodology used throughout the study compared to baseline, the post-baseline values for which the methodology differs from baseline will be discarded in the tables presenting comparisons to baseline.

A listing of patients with newly occurring clinically significant abnormality will be produced.

#### **2.7.4.2 Vital signs**

Vital sign data (blood pressure, heart rate, temperature, etc.) and change from baseline will be listed for each subject by treatment and visit/time. Baseline value will be specified in the listing of vital sign data.

Value of vital signs will be summarized using mean, median, standard deviation, minimum and maximum for baseline and worst-case post-baseline. The change from baseline at each planned visit and worst-case post-baseline will be summarized similarly.

Summary of shift from baseline categories to worst case post-baseline categories will be provided for systolic blood pressure, diastolic blood pressure, temperature and heart rate. Both increase and decrease in the categories will be included. The following categories will be used for both baseline and worst-case post-baseline:

- Systolic blood pressure (mmHg): Grade 0 (<120), Grade 1 (120-139), Grade 2 (140-159), Grade 3/4 ( $\geq 160$ )
- Diastolic blood pressure (mmHg): Grade 0 (<80), Grade 1 (80-89), Grade 2 (90-99), Grade 3/4 ( $\geq 100$ )
- Heart rate: <60bpm, 60-100bpm, >100bpm
- Temperature:  $\leq 35$  C,  $> 35$  to  $< 38$  C,  $\geq 38$  C

Summaries of worst-case post-baseline change from baseline by categories in systolic blood pressure, diastolic blood pressure, temperature and heart rate will be produced:

For heart rate change from baseline category, the following categories will be used:

- Decrease to <60bpm
- Change to normal or no change
- Increase to >100bpm

For temperature change from baseline category, the following categories will be used:

- Decrease to  $\leq 35$
- Change to normal or no change
- Increase to  $\geq 38$

For systolic blood pressure shift from baseline categories, the following categories will be used:

- ‘Any Grade Increase’
- ‘Increase to Grade 1 (120-139 mmHg)’
- ‘Increase to Grade 2 (140-159 mmHg)’
- ‘Increase to Grade 3/4 ( $\geq 160$  mmHg)’

Note: ‘Any Grade Increase’ will include increase to Grade 1 (120-139 mmHg), increase to Grade 2 (140-159 mmHg), and increase to Grade 3/4 ( $\geq 160$  mmHg).

For diastolic blood pressure change from baseline categories, the following categories will be used:

- ‘Any Grade Increase’
- ‘Increase to Grade 1 (80-89 mmHg)’
- ‘Increase to Grade 2 (90-99 mmHg)’
- ‘Increase to Grade 3/4 ( $\geq 100$  mmHg)’

Note: 'Any Grade Increase' will include increase to Grade 1 (80-89 mmHg), increase Grade 2 (90-99 mmHg), and increase to Grade 3/4 ( $\geq 100$  mmHg).

Body weight and change from baseline will be listed. The summary of body weight at baseline and end of study treatment along with percent change will be provided.

## 2.8 Pharmacokinetic endpoints

Plasma concentration data of dabrafenib, dabrafenib metabolites, and trametinib will be listed by subject, and visit/sampling time point. Descriptive summary statistics will be provided by visit/sampling time point. Summary statistics will include mean (arithmetic and geometric), SD, CV (arithmetic and geometric), median, minimum, and maximum. PAS will be used for pharmacokinetics.

## 2.9 PD and PK/PD analyses

Not applicable.

## 2.10 Patient-reported outcomes

Quality of life, as measured by the EORTC-QLQ C30, LC13 and the EQ-5D-5L, will be listed. Descriptive summaries and change from baseline will be provided.

## 2.11 Biomarkers

No biomarker analyses will be presented in this analysis.

## 2.12 Other Exploratory analyses

Not applicable.

## 2.13 Interim analysis

No interim analysis is planned.

11. **What is the primary purpose of the study?**

[figure not shown]
11. **What is the primary purpose of the *Journal of Clinical Endocrinology and Metabolism*?**

\_\_\_\_\_

—  
—

—  
—

© 2013 Pearson Education, Inc.

## **4 Change to protocol specified analyses**

No change from protocol specified analysis was made.

## **5 Appendix**

### **5.1 Imputation rules**

In general imputed partial dates will not be used to derive study day, duration (e.g. duration of adverse events), or elapse time variables. In addition, imputed dates are not used for deriving the last contact date in overall survival analysis dataset.

Imputed dates will not be displayed in listings. However, where necessary, display macros may impute dates as temporary variables for the purpose of sorting data in listings only. In addition, partial dates may be imputed for 'slotting' data to study time periods or for specific analysis purposes as outlined below.

The partial date imputation will follow Analysis Data Model (ADaM) conventions. The ADaM approach is to populate the numeric date variables with the imputed date and add a flag variable to the dataset that indicates the level of imputation. The flag variable can contain the values: blank, 'D', 'M', 'Y'.

blank: indicates that no imputation was done

D='Day': indicates that the day portion of the date is imputed

M='Month': indicates that the month and day portions of the date are imputed

Y='Year': indicates that the entire date (year, month, and day) is imputed.

Details on imputing partial dates for specific datasets are outlined in following sections.

### 5.1.1 Study drug

For patients not known to have died prior to the cut-off date:

- All events with start date before or on the cut-off date, and with end date missing or after the cut-off date will be reported as “continuing at the cut-off date”.
- This approach applies, in particular, to AEs and concomitant medication reports. For these events, the end date will not be imputed and therefore will not appear in the listings.

For patients known to have died prior to or on the cut-off date:

- All events with start date before or on the cut-off date, and with end date missing or after the cut-off date will have the end date imputed to the death date.
- This approach applies, in particular, to AEs and concomitant medication reports. For these events, the imputed end date will not appear in the listings.

If imputation of an end date is required for a specific analysis (e.g. for a dose administration record with missing end date or last date of study drug after the cut-off date), the end date will be imputed to the cut-off date for the purpose of calculating duration of exposure to study drug and dose intensity. The imputed date will be displayed and flagged in the listings.

### 5.1.2 AE date imputation

Date imputation is the creation of a new, complete date from a partial one according to an agreed and acceptable algorithm. Missing date for AE will be handled according to rules specified below. A partial date is simply an incomplete date e.g. DDOCT2001: the days are missing from this DDMMYY YYYY date.

Partial AE start dates, if left partial, would ultimately mean the following

- It would not be possible to place the AE in time.
- Therefore the treatment/dosage at the time of the event would be unknown.
- Therefore the event could not be reported/summarized appropriately – if at all.

Therefore it is important to perform date imputation to ensure that as many data events are represented as correctly as possible. Of course partial and/or missing dates should *also* be caught as edit checks and passed back to the investigator for resolution.

There **will be no** attempt to impute the following:

- **Missing** AE start dates
- AE start dates **missing the year**
- Partial/missing AE **end dates**

The following table explains the abbreviations used.

		Day	Month	Year
Partial Adverse Event Start Date		<not used>	AEM	AEY
Treatment Start Date (TRTSTD)		<not used>	TRTM	TRTY

The following matrix describes the possible combinations and their associated imputations. In the light grey boxes the upper text indicates the imputation and the lower text the relationship of the AE start date to the treatment start date (TRTSTD).

	AEM MISSING	AEM < TRTM	AEM = TRTM	AEM > TRTM
AEY MISSING	NC Uncertain	NC Uncertain	NC Uncertain	NC Uncertain
AEY < TRTY	( D ) Before TRTSTD	( C ) Before TRTSTD	( C ) Before TRTSTD	( C ) Before TRTSTD
AEY = TRTY	( B ) Uncertain	( C ) Before TRTSTD	( B ) Uncertain	( A ) After TRTSTD
AEY > TRTY	( E ) After TRTSTD	( A ) After TRTSTD	( A ) After TRTSTD	( A ) After TRTSTD

The following table is the legend to the above table.

Relationship	
Before TRTSTD	Indicates AE start date prior to Treatment Start Date
After TRTSTD	Indicates AE start date after Treatment Start Date
Uncertain	Insufficient to determine the relationship of AE start date to Treatment Start Date
Imputation Calculation	
NC / Blank	No convention/imputation
( A )	01MONYYYY
( B )	TRTSTD+1
( C )	15MONYYYY
( D )	01JULYYYY
( E )	01JANYYYY

The following table gives a few examples.

Partial AE start date	Treatment start date	Relationship	Imputation Calculation	Imputed Date
12mmYYYY	20OCT2001	Uncertain	NC	<blank>
ddmmm2000	20OCT2001	Before	( D )	01JUL2000
ddmmm2002	20OCT2001	After	( E )	01JAN2002
ddmmm2001	20OCT2001	Uncertain	( B )	21OCT2001
ddSEP2001	20OCT2001	Before	( C )	15SEP2001
ddOCT2001	20OCT2001	Uncertain	( B )	21OCT2001
ddNOV2001	20OCT2001	After	( A )	01NOV2001

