8.1 Screening

Participants must sign an informed consent form (ICF) prior to any study specific screening evaluations, within 28 days prior to the first dose of study treatment. The screening phase begins once written informed consent is provided and ends after 28 days or when participant receives the first dose of study treatment. Following completion of screening procedures and verifying participant eligibility based on assessments, the participant will be enrolled via the Interactive Response Technology (IRT) system. Laboratory results from the local laboratory will be used to determine participant's eligibility to the study. Refer to [Table 8-1](#) for additional details.

For laboratory evaluations used to determine eligibility, a repeated evaluation within the screening window is permitted for screening results out of the defined range. If the repeated laboratory result meets the criteria, that result may be used to determine eligibility. If the repeated laboratory result does not meet the criteria, the patient will be considered a screening failure. Participants who do not meet the criteria for participation in this study (screen failure) may be rescreened once. Each case must be discussed and agreed with Novartis on a case-by-case basis.

All required screening assessments must be repeated if they do not meet the allowed time window for screening, when the subject will be rescreened for participation in the study.

If the participant already provided the ~~archival~~ tumor tissue samples for central testing of *BRAF* V600E mutation status it is not required to submit a new sample

Procedure for re-screening is as follows:

- Site must register the patient as a screen failure in IRT
- Subject number will be different from the initial screening

Adverse events that begin or worsen after informed consent should be recorded in the Adverse Events CRF. Conditions that were already present at the time of informed consent should be recorded in Medical History CRF. CRA is to review and confirm patient's eligibility for re-screening with the site. Patients may be re-screened only once and must be enrolled within 28 days after the recorded rescreening date. All evaluations including original assessments and repeated assessments must be collected on the eCRF.

Participants will be enrolled based on a positive *BRAF* V600E mutation test performed using an NMPA/MOH-approved assay as part of study inclusion criteria ([Section 5.1](#)).

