16.1.4.5.3 Incomplete dates for last known date patient alive or death

All dates must be completed with day, month and year. If the day is missing, the 15th of the month will be used for incomplete death dates or dates of last contact.

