##### End date:

Imputed date = min (start date of study drug, last day of the month), if day is missing;

Imputed date = min (start date of study drug, 31DEC), if month and day are missing.

If the end date is not missing and the imputed start date is after the end date, use the end date as the imputed start date.

If both the start date and the end date are imputed and if the imputed start date is after the imputed end date, use the imputed end date as the imputation for the start date.

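### SAP 5.1.2 rule (B) can date an AE after its own recorded end and count it as treatment-emergent; separately, the SAP's handling of partial last-contact and death dates is not reconciled with the protocol

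*SAP*

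**What the plan says.** **AE start dates.** SAP 5.1.2 compares the month and year of a partial AE start with those of first dose. If the year matches and the month either matches or is missing, rule (B) assigns first dose plus one day. The legend describes these cells as "Insufficient to determine the relationship of AE start date to Treatment Start Date". A start date that is absent, or lacks its year, gets "No convention/imputation". The section warns about starts left partial: "Therefore the event could not be reported/summarized appropriately". It adds that partial or missing dates should "be caught as edit checks and passed back to the investigator for resolution".

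**End-date check.** For prior therapies only, SAP 5.1.3.1 says that if the end date is known and "the imputed start date is after the end date, use the end date as the imputed start date". SAP 5.1.2 has no such step, and SAP 5.1.3 applies the AE conventions to concomitant medication starts.

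**Survival dates.** Protocol 16.1.4.5.3 says: "If the day is missing, the 15th of the month will be used for incomplete death dates or dates of last contact". SAP 2.1.1.5 derives last contact from complete dates. SAP 5.1 says that "imputed dates are not used for deriving the last contact date in overall survival analysis dataset" and, as a general rule, keeps imputed partial dates out of elapsed-time variables. No SAP section gives a rule for a partial death date, SAP 5.1.3.3 (other imputations) is marked not applicable, and SAP section 4 declares no change from the protocol.

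**The concern.** Pre-dose AEs are in the database by design. Protocol 8.1 states: "Adverse events that begin or worsen after informed consent should be recorded in the Adverse Events CRF". Screening can last 28 days. SAP 2.7.1 summarises on-treatment AEs, and protocol 12.5.2 ties this to the start date, so the imputed start decides whether an event enters the treatment-emergent tables. A rule that ignores a recorded end date can therefore move an event that was demonstrably over before dosing into those tables, with an impossible start-after-end record behind it.

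On survival, two documents that are supposed to agree give different instructions for last contact, the OS censoring date. The SAP is also silent on partial death dates, which OS, PFS and DoR all need. If this is left open, a programmer settles it, possibly after seeing the data.

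A lesser gap concerns AEs whose start date or year is still missing once queries are exhausted. No rule places them in, or keeps them out of, the on-treatment tables.

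**Working it through.** **1. Reproduce the SAP's examples.** Applying the 5.1.2 matrix to its seven worked examples (first dose 20OCT2001) returns all seven results. The two rule (B) cases, October 2001 without a day and 2001 without a month, both give 20OCT2001 + 1 = 21OCT2001.

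**2. Add a recorded end date (illustrative dates).** Duration = end − start + 1.
- Start October 2001, end 12OCT2001: imputed start 21OCT2001, which is 21 − 12 = 9 days after the end. Duration = 12 − 21 + 1 = −8 days. Under SAP 2.1.1.6 the event is on-treatment.
- Start 2001 with month missing, end 28SEP2001: imputed start 21OCT2001, which is 2 + 21 = 23 days after the end. Duration = −23 + 1 = −22 days. Again on-treatment.

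**3. Apply the SAP's own cap from 5.1.3.1.** The starts become 12OCT2001 and 28SEP2001, both pre-treatment. An October 2001 start with end 25OCT2001 is untouched: 21OCT2001 is not after the end, so rule (B) still holds and the event stays on-treatment.

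**4. Survival dates side by side.**

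| Date lacking its day | Protocol 16.1.4.5.3 | SAP |
|---|---|---|
| Last contact | 15th of the month | Complete dates only (2.1.1.5, 5.1) |
| Death | 15th of the month | No rule; general bar on imputed dates in elapsed-time variables (5.1) |

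The first row is an explicit contradiction. The second is an omission combined with a general bar that has no written exception for death.

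**5. Why the bare 15th needs a floor.** OS = death − first dose + 1.
- First dose 10JAN2021, death in March 2021: the 15th gives 65 days, against a possible range of 51 (1 March) to 81 (31 March). This is a workable approximation.
- First dose 20OCT2001, death in October 2001: the 15th gives 15 − 20 + 1 = −4 days, which is impossible. Last complete contact cannot be earlier than first dose, so a floor at the day after it gives 21OCT2001 at the earliest, or 21 − 20 + 1 = 2 days.

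**6. Undated AEs.** An AE with no start year and an end date of 05DEC2001, assumed to be during treatment, has a blank start. It falls in none of the three periods in SAP 2.1.1.6, although its end date shows that it was present on treatment.

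**7. Size.** With about 40 participants planned, one participant is 1/40 = 2.5 percentage points. SAP 2.7.1 counts a participant once per AE category, so the shift is 2.5 points if the misplaced event is that participant's only one in the category and zero otherwise.

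**The case against.** Rule (B) is a deliberate and sensible convention: when timing is unknown, the event is counted rather than lost. A reader might infer that the rule itself is wrong. For a first dose on day 20 of a 30-day month, 19/30 = 63% of possible onset days fall before dosing, if onset is equally likely on each day. That is the accepted price of a conservative default. The defect is confined to events whose recorded end date settles the matter. It also requires the query to have failed, and the cap cannot act when the AE end date is partial, because SAP 5.1.2 does not impute those. All of this stands and keeps the point small.

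A reader might also infer that the SAP drops undated AEs. It does not say so. It lists all AEs, sends missing dates back to the site, and is silent on counting what remains unresolved.

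Finally, a reader might conclude that a death known only to the month has no usable date. That is one reading. Protocol 16.1.1 makes section 16.1.4 the source of programming detail for the SAP, SAP section 4 declares no change, and the bar in SAP 5.1 is worded as a general one. SAP silence can therefore be read as leaving the protocol's 15th in force. That argument does not reach last contact, where the SAP is explicit and differs.

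**Conclusion.** The point holds as a minor one. Rule (B), as written, gives a wrong result whenever a recorded AE end date precedes first dose and the partial start falls in the rule (B) cells. Concomitant medications share the gap. The protocol and SAP contradict each other on last contact, and the SAP neither carries over nor exempts the protocol's death-date rule, while stating that nothing changed. Undated AEs are a secondary gap.

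The effect is at most 2.5 percentage points per affected participant per AE category, assuming a denominator of 40, and can be zero. The documents do not show how many records have partial dates; given edit checks, few are likely. A partial death date would affect one participant's OS time and, where death is the event, PFS or DoR. ORR, the primary endpoint, is unaffected.

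**What to change.** Make these changes to the SAP before final database lock:

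1. **5.1.2 and 5.1.3:** add the 5.1.3.1 cap. If the end date is known and the imputed start falls after it, the start becomes the end date. Keep rule (B) as the default when the end date does not settle timing.
2. **5.1:** state that a death date lacking its day is imputed under the protocol's 15th rule for OS, PFS and DoR, but no earlier than the day after the last complete contact and no later than month end or cut-off. Keep complete dates only for last contact.
3. **Section 4:** list both departures from protocol 16.1.4.5.3, namely the floor and limits on the death date and the complete-dates rule for last contact.
4. **5.1.2 (secondary):** count an AE whose start date or year is still missing after query as on-treatment, unless other recorded dates show that it ended before first dose or began more than 30 days after last dose.

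The cost is a few SAP sentences and small programming changes, with no new data collection. AE counts may fall slightly through the cap and rise slightly through the default for undated events.
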